7.3. Premature Withdrawal from the Study

A patient has the right to withdraw from the study at any time, for any reason, and without repercussion.

The investigator and/or sponsor have the right to withdraw a patient from the study if it is no longer in the interest of the patient to continue in the study, or if the patient's continuation in the study places the scientific outcome of the study at risk (eg, if a patient does not or cannot follow study procedures). An excessive rate of withdrawals would render the study uninterpretable; therefore, unnecessary withdrawal of patients should be avoided.

Patients who are withdrawn prematurely from the study will be asked to complete the early termination (ET) visit, and associated end of treatment (EOT) assessments, as described in Section 9.1.3.

Rules for discontinuation of study treatment (permanent or temporary) are discussed in Section 8.4.2.

7.4. Replacement of Patients

Patients prematurely withdrawn from the study can be replaced, if needed, to ensure an adequate number of evaluable patients. The Medical/Study Director, in cooperation with the Study Biostatistician, will decide whether to replace a withdrawn patient.

Patients enrolled and withdrawn from the study any time prior to randomization will not be considered evaluable for assessment and will be replaced with another patient. All patients who have received a dose of study drug will be included in an as treated analysis.

If a patient is replaced after randomization, the replacement patient will receive the randomization assignment of the patient s/he is replacing.

8. STUDY TREATMENTS

8.1. Investigational and Reference Treatments

The REGN4461 dose regimen for this study is mg/kg IV followed by doses of mg SC QW. Placebo product to match to REGN4461 is prepared in the same formulation without the addition of REGN4461. All administration of REGN4461 or placebo is to be performed by study staff and no self-administration of REGN4461 or placebo will occur.

Dosing Schedule:

• **Single-blind run in:** all patients will receive an IV placebo infusion on day -28, followed by placebo SC QW injections administered subsequently for 3 weeks starting on day -21.

• Treatment period 1:

- Study arm 1: IV placebo infusion on day 1 followed by SC QW injections of placebo for 11 weeks starting on day 8
- Study arm 2: IV REGN4461 (mg/kg) infusion on day 1 followed by SC injections of REGN4461 (mg QW) for 11 weeks starting on day 8

• Treatment Period 2:

- Study arm 1: IV REGN4461 (mg/kg) infusion followed by SC placebo on day 85, followed by SC injections of REGN4461 (mg QW) for 11 weeks starting on day 92
- Study arm 2: IV placebo followed by SC injection of REGN4461 (mg mg) on day 85, followed by SC injections of REGN4461 (mg QW) for 11 weeks starting on day 92

Investigational drug formulation and instructions on dose preparation are provided in the pharmacy manual for in-clinic visits and in the nursing manual for remote visits.

8.2. Run-in Treatment

There will be a 4-week single-blind placebo run-in period (day -28 to day -1). At the beginning of the placebo run-in period, patients will receive an IV placebo infusion, followed 1 week later by SC QW injections of placebo, administered for 3 weeks.

8.3. Background Treatment

Standard of care for metabolic abnormalities including stable (ie, no changes within the past 3 months of the screening visit) medications for diabetes and hyperlipidemia.

8.4. Dose Modification and Study Treatment Discontinuation Rules

8.4.1. Dose Modification

After treatment period 1, REGN4461 dose level may be decreased from mg to mg if the following criteria are met:

- 1. for patients with baseline BMI > 20: either BMI < 20 kg/m² OR weight loss > 10%
- 2. for patients with baseline BMI ≤20: in the opinion of the study investigator the weight loss is adverse

For patients with BMI >20 kg/m², any decision to decrease the dose level will be made by the Sponsor, in discussion with the investigator.

If a patient's dose is reduced from mg to mg, their dose cannot be increased during TP2.

8.4.2. Study Drug Discontinuation

Patients who permanently discontinue from study drug before entering TP1 (day 1) will be contacted to assess any adverse events (AEs) but will not be asked to return for the remaining study visits.

Patients who permanently discontinue from study drug after entering TP1 should be encouraged to remain in the study. Those who agree and do not withdraw from the study will be asked to return to the clinic for all remaining study visits per the visit schedule.

Patients who permanently discontinue from study drug and who opt to withdraw from the study will be asked to complete study assessments, per Section 9.1.3.

8.4.2.1. Reasons for Permanent Discontinuation of Study Drug

Study drug dosing will be permanently stopped in the event of:

- Confirmation of pregnancy as evidenced by a positive serum pregnancy test
- Serious or severe allergic reactions considered related to study drug
- Severe liver injury or dysfunction for which no other reason can be found to explain, such as viral hepatitis A, B, or C; preexisting or acute liver disease; or another drug capable of causing the observed injury. Liver injury is defined as follows:
- For individuals with normal baseline transaminase and liver enzyme levels:
 - Alanine aminotransferase (ALT) or aspartate aminotransferase (AST) >8X upper limit of normal (ULN) or
 - ALT or AST >5X ULN on consecutive visits at least 2 weeks apart or
 - ALT or AST >3X ULN and total bilirubin >2X ULN (or international normalized ratio [INR] >1.5)
- For individuals with abnormal baseline transaminase and liver enzyme levels:
 - ALT or AST >3X over baseline and total bilirubin >2X over baseline (or INR >1.5)

- Patient withdraws consent
- Investigator's clinical judgment that it is in the best interest of the patient

8.4.2.2. Reasons for Temporary Discontinuation of Study Drug

The investigator may temporarily discontinue study drug dosing at any time, even without consultation with the medical monitor if the urgency of the situation requires immediate action in the patient's best interest and as clinically indicated. However, the Regeneron medical monitor should be contacted as soon as possible. Resumption of study drug dosing requires consultation and agreement between the investigator and the Regeneron medical monitor.

A special case for temporary discontinuation of study drug relates to a positive urine pregnancy test If there is a positive urine pregnancy test, a confirmatory serum pregnancy test will be performed. Study treatment will not be administered until a negative serum pregnancy test is obtained. If the serum pregnancy test is negative the patient can continue in the study. A positive serum pregnancy test will result in permanent discontinuation of study drug administration.

If a patient requires a prohibited medication at any time during the study, the principal investigator should contact the Regeneron medical monitor (except for illness requiring prompt treatment). Based on the discussions, study drug may be continued or temporarily or permanently discontinued.

8.5. Management of Acute Reactions

8.5.1. Acute Intravenous Infusion Reactions

Emergency equipment and medication for the treatment of infusion reactions must be available for immediate use. All infusion reactions must be reported as AEs (as defined in Section 10.2.4) and graded using the grading scales as instructed in Section 10.3.1.

8.5.1.1. Interruption of the Intravenous Infusion

The infusion should be interrupted if any of the following AEs are observed:

- Sustained/severe cough
- Rigors/chills
- Rash, pruritus (itching)
- Urticaria (hives, welts, wheals)
- Diaphoresis (sweating)
- Hypotension
- Dyspnea (shortness of breath)
- Vomiting
- Flushing

The reaction(s) should be treated symptomatically, and the infusion may be restarted at 50% of the original rate.

If investigators feel there is a medical need for treatment or discontinuation of the infusion other than described above, they should use clinical judgment to provide the appropriate response according to typical clinical practice.

8.5.1.2. Termination of the Intravenous Infusion

The infusion should be terminated and NOT restarted if any of the following AEs occur:

- Anaphylaxis*
- Laryngeal/pharyngeal edema
- Severe bronchospasm
- Chest pain
- Seizure
- Severe hypotension
- Other neurological symptoms (confusion, loss of consciousness, paresthesia, paralysis, etc.)
- Any other symptom or sign that, in the opinion of the investigator, warrants termination of the IV infusion

*Consider anaphylaxis if the following is observed (Sampson, 2006): acute onset of an illness (minutes to several hours) with involvement of the skin, mucosal tissue, or both (eg, generalized hives, pruritus or flushing, swollen lips-tongue-uvula) AND AT LEAST ONE OF THE FOLLOWING:

- Respiratory compromise (eg, dyspnea, wheeze-bronchospasm, stridor, reduced peak expiratory flow, hypoxemia)
- Reduced blood pressure or associated symptoms of end-organ dysfunction (eg, hypotonia [collapse], syncope, incontinence)

8.5.2. Acute Injection Reactions

8.5.2.1. Systemic Injection Reactions

Emergency equipment and medication for the treatment of systemic reactions must be available for immediate use. All injection reactions must be reported as AEs (as defined in Section 10.2.1) and graded using the grading scales as instructed in Section 10.3.1.

Acute systemic reactions following injection of study drug by SC administration should be treated using clinical judgment to determine the appropriate response according to typical clinical practice.

8.5.2.2. Local Injection Site Reactions

Local injection site reactions must be reported as AEs and graded according to Section 10.3.1.

8.6. Method of Treatment Assignment

All patients will enter a 10-week screening period during which screening assessments will be performed, including fasting TG and leptin levels, to determine eligibility. All eligible patients will enter the 4-week single-blind placebo run-in period. Upon completion of the 4-week run-in period, up to 40 patients will be randomized in a 1:1 ratio to study arm 1 (placebo in TP1 and REGN4461 in TP2) or study arm 2 (REGN4461 in TP1 and TP2) according to a central randomization scheme provided by an interactive voice response system (IVRS)/interactive web response system (IWRS) to the designated study pharmacist (or qualified designee). Randomization will be stratified according to HbA1c levels (HbA1c ≤7.0% or HbA1c >7.0% at the screening visit) within each cohort.

8.7. Blinding

Study patients, the principal investigators, and study site personnel will remain blinded to all randomization assignments throughout the study. The Regeneron Medical/Study Director, Study Monitor, and any other Regeneron and contract research organization (CRO) personnel who are in regular contact with the study site will remain blinded to all patient randomization assignments.

Investigators and the sponsor will be blinded to specific endpoints, including, but not limited to HbA1c, fasting glucose, fasting TG and other lipids, and MRI imaging, for the entire length of the treatment period (up to week 24).

Selected individuals not involved in the conduct of the study may have access to unblinded data, as needed, for safety review or other data review.

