6.2. Planned Interim Analysis

No formal interim analysis will be performed in the study. Periodic data reviews may be performed by selected unblinded Sponsor physicians and a statistician with no direct involvement in the study. A first-step analysis will occur after the last patient completes week 12.

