9.1.4. Unscheduled Visits

All attempts should be made to keep patients on the study schedule. Unscheduled visits may be necessary to repeat testing following abnormal laboratory results, for follow-up of AEs, or for any other reason, as warranted. An unscheduled visit may be performed as a remote visit or an outpatient in-clinic visit.

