9.2.4. Laboratory Testing

Detailed instructions for sample collection, along with the location for analysis, are in the laboratory manual provided to study sites.

Samples for laboratory testing will be collected at visits according to Table 1 and Table 2. On study visit days during which study drug will be administered, the laboratory samples are to be collected before the dose of study drug unless otherwise stated.

Fasting is only required for laboratory tests described as "fasting" (eg, fasting TG, fasting lipid panel, and fasting glucose).

Blood Chemistry

Sodium Total protein, serum Total bilirubin
Potassium Creatinine Uric acid

Chloride Blood urea nitrogen (BUN) Creatine phosphokinase (CPK)

Carbon dioxide Aspartate aminotransferase (AST) Gamma-glutamyl transferase (GGT)

Calcium Alanine aminotransferase (ALT) Gamma-glutamyl transferase (GGT)

Fasting Glucose Alkaline phosphatase

Albumin Lactate dehydrogenase (LDH)

Hematology

Hemoglobin Differential:
Hematocrit Neutrophils
Red blood cells (RBCs) Lymphocytes

White blood cells (WBCs)

Red cell indices

Platelet count

Monocytes

Basophils

Eosinophils

Urinalysis

Color Glucose
Clarity Blood
pH Bilirubin

Specific gravity Leukocyte esterase

Ketones Nitrite
Protein WBC

Fasting Lipid Panel

LDL-C Apolipoprotein B HDL-C Triglycerides

Total Cholesterol

Other Laboratory Tests

Fasting Leptin Pregnancy test (serum/urine) Fasting Free Fatty Acids

Hepatitis B surface antigen (sAg) HIV (Ab) HbA1c

Fasting Apolipoprotein C3 Fructosamine Hepatitis C (Ab)

Fasting ANGPTL3 Urine albumin and creatinine

Abnormal Laboratory Values and Laboratory Adverse Events

All laboratory values must be reviewed by the investigator or authorized designee.

Significantly abnormal test results that occur after start of treatment must be repeated to confirm the nature and degree of the abnormality. When necessary, appropriate ancillary investigations should be initiated. If the abnormality fails to resolve or cannot be explained by events or conditions unrelated to the study medication or its administration, the Medical/Study Director must be consulted.

The clinical significance of an abnormal test value, within the context of the disease under study, must be determined by the investigator.

Criteria for reporting laboratory values as an AE are provided in Section 10.1.1.

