10.1.3. Events that Require Expedited Reporting to Sponsor

The following events also require reporting to the sponsor (or designee) within 24 hours of learning of the event.

- SAEs.
- Selected Adverse Events of Special Interest (AESI; serious and nonserious): Adverse events of special interest for this study include the following:
 - Hypoglycemia, defined as blood glucose <54 mg/dL, regardless of symptoms.
 - NODM

For patients with no diabetes at baseline:

a. Two values of fasting (≥8 hours) plasma glucose ≥126 mg/dL (7.0 mmol) during the treatment period

OR

b. Two values of HbA1c ≥6.5% (48 mmol/mol) during the treatment period

Patients who meet either of these criteria during the placebo run-in period will be considered to have diabetes at baseline.

- Hyperglycemia requiring treatment, defined as:
- a. HbA1c ≥10.5% AND increase in HbA1c of ≥1.5% from baseline value OR
- b. Fasting glucose ≥250 mg/dL on 2 occasions including symptoms consistent with hyperglycemia AND increase in fasting glucose >50 mg/dL above baseline
 - Development of new or worsening of autoimmune disease

- Moderate or severe hypersensitivity reactions
- Moderate or severe infusion reactions

Other Events that Require Accelerated Reporting to Sponsor

The following events also require reporting to the sponsor (or designee) within 24 hours of learning of the event:

- **Pregnancy:** Although pregnancy is not considered an AE, it is the responsibility of the investigator to report to the sponsor (or designee), within 24 hours of identification, any pregnancy occurring in a female or female partner of a male, during the study or within 16 weeks of the last dose of study drug. Any complication of pregnancy affecting a female study patient or female partner of a male study patient, and/or fetus and/or newborn that meets the SAE criteria must be reported as an SAE. Outcome for all pregnancies should be reported to the sponsor.
- **Symptomatic Overdose**: Accidental or intentional overdose of at least 2 times the intended dose of study drug within the intended therapeutic window, if associated with an AE.

For the AESIs based on a laboratory value, the AESI must be reported to Sponsor within 24 hours once the investigator confirms the abnormal laboratory value.

10.1.4. Other Adverse Events of Special Interest that Do Not Require Expedited Reporting to Sponsor

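### Protocol 8.7 masks HbA1c and fasting glucose to week 24 with no alert route to the investigator, whose confirmation starts 24-hour reporting of laboratory AESIs

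*Protocol*

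**What the plan says.** **Masking.** Protocol 8.7: "Investigators and the sponsor will be blinded to specific endpoints, including, but not limited to HbA1c, fasting glucose, fasting TG and other lipids". MRI is on the same list, and the masking lasts through week 24.

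**Who may look.** The same section adds: "Selected individuals not involved in the conduct of the study may have access to unblinded data, as needed, for safety review". Section 6.2 adds: "Periodic data reviews may be performed by selected unblinded Sponsor physicians and a statistician with no direct involvement in the study".

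**Reporting.** For AESIs based on a laboratory value, Protocol 10.1.3 says that "the AESI must be reported to Sponsor within 24 hours once the investigator confirms the abnormal laboratory value". One criterion for hyperglycemia requiring treatment is "HbA1c ≥10.5% AND increase in HbA1c of ≥1.5% from baseline value". New-onset diabetes mellitus (NODM), in patients without diabetes at baseline, is two fasting plasma glucose values of at least 126 mg/dL or two HbA1c values of at least 6.5% in the treatment period.

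**Laboratory review.** Protocol 9.2.4: "All laboratory values must be reviewed by the investigator or authorized designee". It continues: "Significantly abnormal test results that occur after start of treatment must be repeated to confirm the nature and degree of the abnormality". Section 9.1.4 provides for the visits: "Unscheduled visits may be necessary to repeat testing following abnormal laboratory results".

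**Analysis.** SAP 4.8.1.2 and Table 19 identify hypoglycemia, NODM and hyperglycemia from both the eCRF and laboratory data. SAP 5.8.2 summarises AESIs by frequency without separating the two sources. SAP 1.2.4 records that the study was terminated early with limited enrolment.

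**The concern.** Section 8.7 withholds a result that 10.1.3 needs the investigator to confirm and 9.2.4 needs the investigator or designee to review. Neither of the latter sections makes an exception for masked analytes.

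This is more than missing operational detail. Section 3.3.1 names hypoglycemia and hyperglycemia as risks and gives expedited AESI reporting, NODM included, as the response. A rule in 8.7 defeats part of that safeguard. At stake is how soon the investigator learns of new diabetes or a marked HbA1c rise, and how soon the sponsor receives the report. The efficacy analysis is not affected.

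**Working it through.** The plan states no figure on this point. The check compares the sections and then counts weeks.

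**Step 1. Which laboratory criteria in 10.1.3 depend on masked results?**

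| Criterion | Masked analyte needed? | Other way to notice |
|---|---|---|
| Hypoglycemia, glucose <54 mg/dL | Not necessarily; any blood glucose counts | Glucometer |
| NODM, two fasting glucose ≥126 mg/dL | Yes | Separately ordered test only |
| NODM, two HbA1c ≥6.5% | Yes | Separately ordered test only |
| Hyperglycemia, HbA1c ≥10.5% and rise ≥1.5% | Yes | Separately ordered test only |
| Hyperglycemia, fasting glucose ≥250 mg/dL twice with symptoms and rise >50 mg/dL | Yes | Symptoms or glucometer may prompt a test |

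The problem is sharpest for the three middle criteria. Glucometer self-monitoring (9.2.3.6) is recommended only for diabetic patients on insulin or secretagogues, so it does not cover patients without diabetes at baseline, and it does not measure HbA1c. Urinalysis glucose and fructosamine may hint at worsening but cannot meet any of the three.

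**Step 2. Does another section carry a masked result to the site?**

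- 8.7 and 6.2: review is optional, by people outside study conduct, with no threshold, timing or message to the site.
- 8.8: emergency unblinding releases treatment assignment, not laboratory results.
- 9.1.4: repeat visits are possible, but someone must first know that a result is abnormal.
- 10.4: the sponsor monitors safety, but 8.7 masks the sponsor too, and no exception is written for the Medical/Study Director.
- 9.2.4: the laboratory manual is described as covering sample collection and location of analysis. Whether it holds alert values cannot be seen.

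**Step 3. How long could a result stay masked?** Inputs are the nominal weeks in Protocol Table 2, after day 1 (a pre-dose sample) and before week 24.

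- HbA1c row: 4, 6, 10, 12, 16, 18, 22 = 7 weeks.
- Fasting-glucose row: 2, 4, 6, 8, 10, 11, 12, 14, 16, 18, 20, 22, 23 = 13 weeks.
- Blood-chemistry row, whose panel lists fasting glucose: 1, 3, 6, 8, 10, 12, 13, 15, 17, 18, 20, 22 = 12 weeks. Weeks 1, 3, 13, 15 and 17 are not on the glucose row, so the union is 13 + 5 = 18.

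Longest delay = 24 − first week at which the criterion can be met:

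- One HbA1c ≥10.5% with the rise, week 4: 24 − 4 = 20 weeks.
- Second HbA1c ≥6.5%, week 6: 24 − 6 = 18 weeks.
- Second fasting glucose ≥126 mg/dL, glucose row (weeks 2 and 4): 24 − 4 = 20 weeks.
- The same, if chemistry glucose is fasting and masked (weeks 1 and 2): 24 − 2 = 22 weeks.

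If chemistry glucose were left unmasked, 12 of the 18 glucose weeks would be visible but none of the 7 HbA1c weeks.

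**Step 4. How many patients could be affected?** The HbA1c ≥10.5% criterion can apply to any of the planned 40. The number eligible for NODM is not given. Protocol 11.2 expects 78% to have HbA1c >7.0%. Assuming that this share holds in both cohorts and that all of those patients count as diabetic at baseline, at most (1 − 0.78) × 40 = 8.8, about 9, remain eligible. Known diabetes with HbA1c of 7.0% or less, and patients reclassified as diabetic in the run-in, would lower that.

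**The case against.** A reader might infer that 8.7 has no safety exception at all. The text does not support that: its next paragraph allows safety review of unblinded data, and 6.2 names unblinded sponsor physicians. What is missing is the route from those reviewers to the investigator.

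A reader might also infer that the 24-hour report can never start. That is too strong. Nothing in 8.7 forbids an investigator to order a glucose or HbA1c test on clinical grounds, the criteria do not say that the value must come from a masked sample, and 9.1.4 allows unscheduled visits for any warranted reason. Antidiabetic monitoring takes place at every weekly visit. Fructosamine, which 8.7 does not name, is drawn at 11 weeks between day 1 and week 24 and could prompt a test, though the open-ended masking list leaves its status unclear. Section 10.1.3 also counts the 24 hours from learning of the event, so an unseen value breaches no reporting rule. All of this stands, and it limits the point to recognition from scheduled study samples.

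The effect on care can also be doubted. Rescue treatment in 8.10.2 is tied to symptomatic fasting glucose of 250 mg/dL or more, not to HbA1c, and the NODM criteria probably concern a small minority. That reduces the size but does not reconcile the sections.

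Finally, alert values may sit in the laboratory manual. That is possible, but 8.7 as written leaves the investigator masked, and the described scope of the manual does not mention alerts.

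**Conclusion.** The conflict is real and worth fixing. Before week 24, scheduled study samples do not let the investigator recognise NODM or the HbA1c ≥10.5% criterion, although the investigator's confirmation starts the expedited report. The worst-case delays are 20, 18 and 20 weeks. The 22-week and 18-draw figures require chemistry-panel glucose to be fasting and masked. The panel labels it fasting, but the chemistry row in Table 2 carries no fasting footnote. These are upper limits from nominal visits, not expected delays.

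The harm is to timely recognition and reporting. It would be wrong to conclude that AESI totals are biased, because SAP 4.8.1.2 and Table 19 derive these events from laboratory data whether or not a site reported them. Early termination (SAP 1.2.4) reduces the remaining practical impact. The conclusion assumes that no alert arrangement exists outside the two documents.

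**What to change.** While any patient is on treatment:

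1. Add to Protocol 8.7 that the central laboratory, or the unblinded safety reviewers it already allows, alerts the investigator when a patient meets a 10.1.3 laboratory threshold. Cover at least the two NODM criteria, with a baseline-diabetes flag, and the HbA1c ≥10.5% criterion.
2. State in 10.1.3 that receipt of the alert starts the 24-hour clock.
3. Limit the 9.2.4 review duty to unmasked analytes plus these alerts.
4. Say whether chemistry-panel glucose is masked.

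The cost is protocol wording, an alert set-up at the laboratory and a named sender. No new samples or visits are needed. The downside is that extreme values are disclosed for a few patients.

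If no patient remains on treatment, an optional fallback is to show investigator-reported and laboratory-derived-only AESIs separately in the SAP 5.8.2 table. Both sources are already specified, so this needs no new data, and it would show whether events went unreported in real time.
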